### 11.2 Device Deficiency

The DD definition is provided in Table 5. DD information will be collected throughout the study and reported to Medtronic. Note that DD that result in an AE to the subject should be captured as an AE only.

DD that did not lead to an AE but could have led to a SADE (i.e., if suitable action had not been taken, if intervention had not been made, or if the circumstances had been less fortunate) require immediate (no later than 72 hours of the investigator's/site's first knowledge of the event) reporting on a Device Deficiency eCRF (see Table 7).

### 11.3 Processing Updates and Resolution

[figure not shown]
For any changes in status of a previously reported adverse event or DD (i.e. change in actions taken, change in outcome, change in relatedness), information needs to be updated on, or added to the original AE or DD form. All AEs must be followed until the AE has been resolved, is unresolved with no further actions planned, the subject dies or exits the study, or until study closure, whichever occurs first.

In the event that a subject is exited from the study prior to study completion, all efforts should be made to continue following the subject until all unresolved AEs are resolved, unresolved with no further actions planned, or site closure, whichever occurs first.

At the time of study exit, all collected adverse events that are unresolved must be reviewed and an update to the original AE must be reported.

### 11.4 Definitions/Classifications

For the purpose of this clinical study, Medtronic shall define and classify the following events per ISO14155:2020 and 21 CFR 812.3. Note that these regulations are used for definitions only. the study is not following either for reporting requirements as this is a post market surveillance study following 21 CFR 822.

**Table 5: Adverse Event and Device Deficiency Definitions**

Event Type	Definition
Adverse Event (AE) (ISO 14155:2020, 3.2)	
Untoward medical occurrence, unintended disease or injury, or untoward clinical signs (including abnormal laboratory findings) in subjects, users or other persons, whether or not related to the investigational medical device and whether anticipated or unanticipated
 
NOTE 1: This definition includes events related to the investigational medical device or the comparator.
 
NOTE 2: This definition includes events related to the procedures involved.
 
NOTE 3: For users or other persons, this definition is restricted to events related to investigational medical devices.

Serious Adverse Event (SAE) (ISO 14155:2020, 3.45)	
AE that led to any of the following
 
 
a) death,
 
b) serious deterioration in the health of the subject, users or other persons as defined by one or more of the following:               
 
1) a life-threatening illness or injury, or
 
2) a permanent impairment of a body structure or a body function, including chronic disease, or
 
3) in-patient or prolonged hospitalization, or
 
4) medical or surgical intervention to prevent life-threatening illness or injury or permanent impairment to a body structure or a body function,
 
 
 
c) fetal distress, fetal death or a congenital abnormality or birth defect including physical or mental impairment
 
 
NOTE 1: Planned hospitalization for a pre-existing condition, or a procedure required by the CIP, without serious deterioration in health, is not considered an SAE.

Adverse Device Effect (ADE) (ISO 14155:2020, 3.1)	
AE related to the use of an investigational medical device
 
NOTE 1: This definition includes AEs resulting from insufficient or inadequate instructions for use, deployment, implantation, installation, or operation, or any malfunction of the investigational medical device.
 
NOTE 2: This definition includes any event resulting from an error use or from intentional misuse of the investigational medical device.
 
NOTE 3: this includes 'comparator' if the comparator is a medical device.

Serious Adverse Device Effect (SADE) (ISO 14155:2020, 3.44)	
Adverse device effect that has resulted in any of the consequences characteristic of a serious adverse event.

# Ellipsys Vascular Access System Post Market Surveillance Study Clinical Investigation Plan

MDT20052

Version 4.0

Page 37 of 64

Medtronic

Unanticipated Adverse Device Effect (UADE) (21 CFR 812.3(s))	Any serious adverse effect on health or safety or any life-threatening problem or death caused by, or associated with, a device, if that effect, problem, or death, was not previously identified in a nature, severity, or degree of incidence in the investigational plan or application (including a supplementary plan or application), or any other unanticipated serious problem associated with a device that relates to the rights, safety, or welfare of subjects.
Device Deficiency (ISO 14155:2020, 3.19)	
Inadequacy of a medical device with respect to its identity, quality, durability, reliability, usability, safety or performance.
 
NOTE 1: DD include malfunctions, use errors and inadequacy in the information supplied by the manufacturer including labeling.
 
NOTE2: This definition includes device deficiencies related to the investigational medical device or the comparator.

For each reported AE, the causal relationship between the AE, the study device and the study procedure shall be classified as not related, possible, probable, or causal.

The causal relationships for device-related and procedure-related are defined in Table 6.

**Table 6: Adverse Event Causal Relationship Definitions**

Related to	Definition
Ellipsys System	Adverse events directly attributable to use of the device including introduction, use and removal from the vessel.
Study (Index) Procedure	
Adverse events that occur within 30 days of the index procedure where the Ellipsys System was used unless specifically shown not to be related to that index procedure.
 
Except the introduction, use and removal of the device including:
 
 
- initially accessing the vessel
 
- any catheter/wire exchanges during the study procedure not directly involving the study device, e.g., related to a completion angiogram
 

Secondary Procedure	Adverse events directly related to any aspect of the secondary procedure except the introduction, use and removal of device.
Intra-procedure (Index) PTA/balloon angioplasty or Planned PTA/balloon Maturation Procedure	
Adverse events directly related to the intra-procedure (index) or planned PTA/balloon maturation procedure (peri-procedure AEs and late AEs) including:
 
 
- introducing, inflating, deflating or removing the balloon catheter
 
- intimal injury, acute anastomotic disruption, extravasation, hematoma, pseudoaneurysm
 
- peri-anastomotic stenosis, intimal hyperplastic lesions
 

**Medtronic Business Restricted**

**CONFIDENTIAL**

056-F275 Rev E Clinical Investigation Plan Template

	NOTE: As stated in the Ellipsys System IFU (available separate from the CIP), PTA/balloon maturation procedures to increase flow to the optimal access vessel was required in 99% of the Ellipsys IDE study subjects overall. The majority of these were performed to increase the anastomosis and juxta-anastomotic diameter and were unrelated to any clinical pathology. It is expected that similar procedures will be performed by the study investigator post-procedure and designated as such on the Secondary Procedure Form.
Cannulation	Adverse events directly related to cannulating a mature AV fistula target vessel to conduct dialysis, or other complications that can occur during or after dialysis such as bleeding, hematoma, etc.

## 11.5 Reporting of Adverse Events

The investigator is required to assess and document in the medical record all SAEs, ADEs, SADEs, and DDs (per the definitions in Table 5) observed in subjects from the time of study enrollment. AEs shall be followed until the event has resolved or until study exit. In case of permanent impairment, the event shall be followed until the event stabilizes and the overall clinical outcome has been ascertained.

Reporting of AEs and DDs shall end once the subject exits the study. In any case where AEs are unresolved at the time of study exit, this shall be documented on the eCRF.

The investigator is responsible for reporting AEs to Medtronic and their local IRB (per IRB reporting requirements) as outlined in Table 7 below, by completing the Adverse Event eCRF and/or Device Deficiency eCRF. For the purposes of this CIP, planned/elective procedures for pre-existing conditions are not considered or reported as AEs as long as the pre-existing condition is not aggravated or exacerbated after a study procedure. A list of AEs that may be associated with the device and/or the interventional procedure is provided in Section 10.1.

**Table 7: Adverse Event Reporting Guidelines (Site Reporting to Medtronic\*)**

Event Type	Timeframe for Event Reporting	Requirement for Event to be Reported
Serious Adverse Event (SAE)	As soon as possible, but within 10 working days from the investigator's/site's first knowledge of the event	Through Study Exit
Adverse Device Effect (ADE)		
Serious Adverse Device Effect (SADE)		
Device Deficiency (DD)		
Device Deficiency (DD) that did not lead to AE but could have led to a SADE	Immediately or no later than 72 hours from the investigator's/sites' first knowledge of the event	Through Study Exit

\*Study sites are responsible for reporting AEs/Device Deficiencies to the IRB per the IRB reporting policy

**Medtronic Business Restricted**

**CONFIDENTIAL**

056-F275 Rev E Clinical Investigation Plan Template

For any study related emergency, the investigators can contact the Medtronic Clinical Research Specialist assigned to the site, or any member of the Medtronic clinical study team. Contact information for the clinical study team are listed on the Study Contact List in the Investigator Site File.

## 11.6 Product Complaint Reporting

It is the responsibility of the investigator to report all product complaint(s) associated with a medical device distributed by Medtronic, regardless of whether they are related to intended use, misuse or abuse of the product. Reporting must be done immediately and via the regular channels for market-released products. The reporting of product complaints by the clinical team must be done according to the local Standard Operating Procedures. Medtronic will notify the FDA as required per applicable regulations.

## 12. Data Review Committees

---

### 12.1 Clinical Events Committee Review

The Clinical Events Committee (CEC) is an independent committee of medical experts established to assess important endpoints of the study and determine whether each meet protocol-specified criteria. These endpoints may include certain categories of adverse events or other occurrences that arise during the study. The CEC reviews pertinent subject data, including, but not limited to, the patient medical chart, laboratory or pathology findings, imaging data, postmortem reports, and other relevant data for subjects participating in the study.

The CEC will consist of a minimum of three (3) non-Medtronic employed physicians that are not participating investigators for the study, including a CEC chairperson. The CEC is charged with the categorization of selected adverse events and clinical endpoints in the study, using criteria established at the outset of the study and specified by the CIP and the CEC Charter.

Database automated alerts and the independent Medical Monitor at Medtronic's designated Contract Research Organization (CRO) will identify clinical events requiring adjudication as specified in the CEC Charter. The CEC will regularly evaluate and adjudicate these events, as well as other events as may be requested by Medtronic.

The CEC will be established and led by:

Syntactx  
[name]  
[name]  
New York, NY 10007

### 12.2 Duplex Ultrasound Core Lab

The Duplex Ultrasound Core Laboratory (DUS Core lab) is responsible for developing protocol requirements, reviewing DUS exams, interpreting subject DUS data, and providing feedback on the quality of the DUS exams to participating sites. The DUS Core lab shall review, analyze, and record data

***Medtronic Business Restricted***

**CONFIDENTIAL**

056-F275 Rev E Clinical Investigation Plan Template

on the Duplex Core laboratory Assessment eCRF. The DUS Core laboratory's interpretation of all DUS exams shall be used for the data analyses.

The DUS Core lab responsible for analyzing all DUS exams is:

Vascular Ultrasound Core Laboratory (VasCore)  
Massachusetts General Hospital  
[name]  
Boston, MA 02114

## 13. Statistical Design and Methods

This is a prospective, non-randomized, multi-center post-market surveillance study using newly trained study sites. The objective of this post-market surveillance study is to further support the short-term safety of the device and procedure and the long-term safety and effectiveness in subjects treated by newly trained providers of the Ellipsys Vascular Access System in the creation of a native AV fistula (AVF) via percutaneous access in subjects who are on hemodialysis and are medically indicated for the creation of an upper limb anastomosis.

General methods as well as methods used for each study objective are outlined below. To assess the continued safety of the AVF creation procedure post-market, a subset of study safety endpoints will be descriptively compared to the pre-market study (DEN170004) results where possible. Further details will be documented in the Statistical Analysis Plan (SAP). Any deviation to the pre-specified statistical analyses will be noted in the study final report.

### 13.1 General Aspects of Analysis

Data analysis will be performed by Medtronic employed statisticians. All statistical analyses will be generated using SAS version 9.4 or later or R version 4.0 or later software. Demographic and baseline characteristics will be summarized descriptively and will include age, gender, ethnicity, race, body mass index and relevant co-morbidities (including diabetes and hypertension). For continuous variables, descriptive statistics will be presented including the number of subjects with the measurement, mean, standard deviation, median, minimum and maximum. For categorical variables, descriptive statistics will include the number with the characteristic, the number evaluated, and the percentage.

Subject enrollment and accountability, visit attendance, and end of study status will be displayed using a STROBE diagram and descriptive statistics, as appropriate. At each study visit, the following information will be tallied: completed visits, missed visits, deaths, study withdrawals, and lost to follow-up. Compliance with study visits will be summarized as the percent of subjects available at each visit.

The study populations are defined as follows:

1. The **Safety population** is defined as all enrolled subjects in whom the procedure has been attempted and the Ellipsys Device deployed, whether successful or not.

2. The **Treated population** is defined as all subjects in the Safety population with AVF successfully created.

Subject status will be presented for all enrolled subjects. Summaries of baseline parameters will be based on the Safety population. Summaries of the primary safety analyses will be based on the Safety population. Primary effectiveness and secondary endpoint analyses will be based on the Safety and/or Treated population, as indicated in the following sections.

Missing data for the primary endpoints may result from a study procedure attempted but not completed, or loss to follow-up or death prior to endpoint assessment. In time-to-event analysis, where applicable, patients lost to follow-up or who have died will be treated as censored or as a competing risk for observation of the primary endpoint.

Missing data for secondary endpoints may result from clinical assessments unable to be performed due to a remote visit, or unanswered questions on the Subject and Cannulator Satisfaction surveys. Additionally, ultrasound measurements of artery and vein diameters and mean flow rates may be unavailable due to normal variations in subject anatomy. These missing values will be excluded from summaries and analyses. In general, imputation of missing data will not be performed for descriptive statistics.

In general, although this post-market study has multiple primary endpoints, they are not hypothesis-driven and therefore their results will be presented descriptively with no adjustments for multiple comparisons. For comparisons between pre-market results and post-market results, however, these comparisons will account for multiple comparisons. Two comparisons between the pre-market study (DEN170004) and the post-market study are anticipated, for Primary Safety Objective #1, and components of Secondary Objective #4. A Bonferroni adjustment to the alpha-level to determine the quantile for the confidence intervals in those analysis will be performed. Thus, confidence intervals for these comparisons will be based on 97.5% confidence intervals rather than 95% confidence intervals.

## 13.2 Primary Objective(s)

There are no formal hypothesis tests or sample size requirements for the primary objectives.

### 13.2.1 Primary Safety Objective #1

#### *Early Occlusion*

#### **Endpoint Definition:**

Early occlusion is defined as the percentage of subjects with total occlusion within 7 days ( $\leq 7$ ) of the AVF creation procedure. These events will be based on the adjudication by an independent CEC.

#### **Analysis Method:**

Early occlusion will be summarized by presenting the number, percentage, and two-sided 95% CI for the percentage of subjects with early occlusion. Early occlusion will be presented overall and separately by type and location of the occlusion.

***Medtronic Business Restricted***

**CONFIDENTIAL**

056-F275 Rev E Clinical Investigation Plan Template

**Determination of Subjects/Data for Analysis:**

Safety Analysis Set

**Additional Analysis:**

To assess the short-term safety of the AVF creation procedure, early occlusion will be descriptively compared to the pre-market study (DEN170004). Early occlusion will be compared using the percentage and 97.5% CI for each study (CI adjusted for multiple comparisons). If there are differing representations of baseline characteristics between the two studies, they will be adjusted for in the analysis.

### 13.2.2 Primary Safety Objective #2

*Study related serious adverse events through 12 months*

**Endpoint Definition:**

The rate of SAEs through 12 months related to the device, study procedure, or secondary procedure to maintain or re-establish patency. For time-to-event analysis, day 0 is day of first attempted AVF creation procedure and final date is day of event or day of last follow-up. An independent CEC will assess and adjudicate any potential relationship to the device and/or procedures per the criteria set in the CEC charter.

**Analysis Method:**

The study-related SAE rate will be summarized for the Safety population using a Kaplan-Meier curve through at least 12 months. Analyses will include survival probabilities and 95% confidence interval bands through the 12-month visit. Subjects not completing the study will be censored after their last available visit. A sensitivity analysis shall be performed where a cumulative incidence curve is estimated and death will be accounted for as a competing risk.

**Determination of Subjects/Data for Analysis:**

Safety Analysis Set

### 13.2.3 Primary Effectiveness Objective

*Cumulative Patency through 12 months post AVF creation*

**Endpoint Definition:**

Cumulative patency is defined as freedom from access abandonment from time of access creation. An abandoned dialysis access is one that can no longer be used for one or two needle prescribed dialysis because it is unable to provide adequate blood flow and/or is deemed unsafe for the patient, and the associated problem cannot be corrected by any intervention either medical, endovascular or surgical.

**Analysis Method:**

Cumulative patency will be summarized for the Treated population using a Kaplan-Meier curve through at least 12 months. Analyses will include patency/survival probabilities and 95% confidence interval bands through the 12-month visit. Subjects not completing the study will be censored after their last

**Medtronic Business Restricted**

**CONFIDENTIAL**

056-F275 Rev E Clinical Investigation Plan Template

available visit. A sensitivity analysis shall be performed where a cumulative incidence curve is estimated and death will be accounted for as a competing risk.

## Determination of Subjects/Data for Analysis:

Treated Analysis Set

## Additional Analysis:

- Cumulative patency post- surgical or endovascular intervention
- The association between early occlusion and cumulative patency through 12 months will be summarized for the Treated population. Kaplan-Meier curves and associated life tables will be generated summarizing cumulative patency comparing curves for subjects who experience and do not experience early occlusions.

The association between the number of secondary procedures required to facilitate maturation or maintain the functionality of a patent access and cumulative patency through 12 months will be summarized for the Treated population. Kaplan-Meier curves and associated life tables will be generated summarizing cumulative patency for subjects having 0, 1, 2, 3 and 4 or more secondary procedures.

## 13.3 Secondary Objectives

There are no formal hypothesis tests or sample size requirements for the secondary objectives.

### 13.3.1 Secondary Objective #1

*Primary Patency through 12 months post AVF creation*

#### Endpoint Definition:

Primary patency is defined as freedom from access thrombosis or any intervention designed to facilitate, maintain or re-establish patency in a thrombosed access from time of access creation. Subsequent to completion of the AVF creation procedure, consistent with the Training Manual for this staged procedure, the site investigator will assess if an additional PTA balloon maturation or other procedure is needed to promote maturation when outflow is <400 ml/min. Therefore, these specific maturation procedures will not be included in the primary patency endpoint.

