#### 1. Primary Patency Through 12 months Post-AVF Creation:

Defined as freedom from access thrombosis or any intervention designed to facilitate, maintain or re-establish patency measured from time of access creation through 12 months.

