**Endpoint Definition:**

Assisted primary patency is defined as freedom from access thrombosis from time of access creation.

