4.2.1 Secondary Endpoints

The following secondary endpoints to be evaluated in this study are as follows:

1. Primary patency through 12 months post-AVF creation:

Defined as freedom from access thrombosis or any intervention designed to facilitate, maintain or reestablish patency measured from time of access creation through 12 months.

2. Assisted primary patency through 12 months post-AVF creation:
Defined as freedom from access thrombosis from time of access creation through 12 months.
3. Secondary procedure Rate:
Defined as the percentage of subjects having one or more surgical or percutaneous interventions designed to mature or maintain the AVF or re-establish flow. Secondary procedures are procedures subsequent to completion of the AVF creation procedure. This endpoint will also be summarized by type of procedure, indication, procedure success and association with any adverse events (AEs).
4. Overall patient safety:
A full characterization of all adverse events during the study.

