7.7.2 Secondary Objective #1

Primary Patency through 12 months post AVF creation

Analysis Dataset:

Treated Analysis Set per section **Error! Reference source not found..**

Analysis Method:

Primary patency will be summarized for the Treated population using a Kaplan-Meier curve through at least 12 months. Analyses will include patency/survival probabilities and 95% confidence interval bands through the 12-month visit. The confidence interval will be calculated using a typical transformation of the survival function: $\log(S(t))$. Subjects not completing the study will be censored after their last available patency assessment. A sensitivity analysis shall be performed where a cumulative incidence curve is estimated and death will be accounted for as a competing risk. The cumulative incidence curve will be descriptively compared to $1-S(t)$ where $S(t)$ is the survival function estimated by the Kaplan-Meier method.

The observed cumulative incidence estimate may be calculated using the “cmprsk” library in R, with code similar to the following:

```
cmpout1 <- cuminc(time,event)
```

The event variable is 0 if censored, 1 if an event occurs and 2 if a death occurs. Similar analysis will be conducted on the subcomponents of the endpoint.

Endpoint Definition:

Primary patency is defined as freedom from access thrombosis or any intervention designed to facilitate, maintain or reestablish patency in a thrombosed access from time of access creation. Subsequent to the completion of the AVF creation procedure, consistent with the Training Manual for this staged procedure, the site investigator will assess if an additional PTA balloon maturation or other procedure is needed to promote maturation when outflow is <400 ml/min. Therefore, these specific maturation procedures will not be included in the primary patency endpoint. For time-to-event analysis, day 0 is time of access creation and final date is day of event or day of last follow-up. The definition of primary patency is derived from reporting standards by Sidawy, et al and Shenoy, et al [1,2].

Additional Analysis:

- Primary patency post- surgical or endovascular intervention

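### Primary patency is defined in two incompatible ways, and the analysis wording leaves unclear whether an intervention in an open access is an event

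*Protocol*

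**What the plan says.** Each document defines primary patency twice.

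- **Endpoint lists.** Protocol 4.1.4 gives "freedom from access thrombosis or any intervention designed to facilitate, maintain or re-establish patency measured from time of access creation through 12 months". SAP 4.2.1 matches it apart from a hyphen. Neither limits the state of the access or exempts any kind of procedure.
- **Analysis sections.** In Protocol 13.3.1 the intervention limb becomes "any intervention designed to facilitate, maintain or re-establish patency in a thrombosed access from time of access creation"; SAP 7.7.2 has the same limb, "any intervention designed to facilitate, maintain or reestablish patency in a thrombosed access from time of access creation". Both then say that balloon PTA maturation, or another procedure to promote maturation when outflow is below 400 ml/min, is not counted.

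Three other places bear on the reading. Protocol 13.3.2 states: "Assisted primary patency is defined as freedom from access thrombosis from time of access creation". The note in Table 6 of Protocol 11.4 reports that PTA/balloon maturation "was required in 99% of the Ellipsys IDE study subjects overall", and expects similar procedures after the index procedure in this study. SAP 10.1 says that Section 7 holds the endpoint definitions for all objectives.

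**The concern.** The two definitions do not count the same events. The endpoint lists make a planned balloon maturation an event; the analysis sections exempt it. The analysis sections also add the thrombosed-access qualifier, which can be read as attaching to all three verbs (facilitate, maintain, re-establish) or to the last one only. The choice decides whether a PTA for stenosis in an access that is still open, say at month 8, ends primary patency.

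The study tests no hypotheses, so the estimates are its output, and they go to FDA in the interim and final reports (Protocol 15.8.2). Protocol 13 promises that deviations from the pre-specified analyses will be noted in the final report. With two definitions pre-specified, it is unclear what would count as a deviation. SAP 7.9 lists no changes to the planned analysis, so the difference is not acknowledged.

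**Working it through.** **Inputs.** The four definitions and the assisted-patency definition, as above, and the 99% from the Table 6 note, which comes without numerator, denominator or timing. The plan states no expected primary patency, so there is no figure of its own to reproduce. Its enrolment figure does reproduce (100/0.75 = 133.3, rounded up to 134), and the point does not rest on it.

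**Step 1: event times under the analysis wording.** Let T be the time of first thrombosis and V the time of the first intervention that counts. Primary patency ends at min(T, V); assisted primary patency ends at T.

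- Qualifier on all three verbs: an intervention counts only in an access that has already thrombosed, so V ≥ T and min(T, V) = T. The intervention limb adds no events, and Secondary Objectives #1 and #2 coincide for every subject.
- Qualifier on the last verb only: an intervention to facilitate or maintain patency in an open access counts, V can precede T, and the two endpoints differ.

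**Step 2: which reading fits the rest of the text.** Protocol 13.3.1 and SAP 7.7.2 go on to exempt maturation procedures, which would be pointless if only interventions in thrombosed accesses counted. SAP 7.7.2 also plans an analysis of the endpoint's subcomponents; under the first reading the intervention component could never be a first event. Both favour the second reading.

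**Step 3: the Section 4 wording.** Assume that maturation PTA counts as facilitating patency (the analysis sections would not need to exempt it otherwise) and that this study repeats the pre-market 99%. Let f be the share of those subjects whose PTA comes after completion of the creation procedure. With complete follow-up, the intervention limb alone caps 12-month primary patency at 1 − 0.99f:

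| f | Cap | Of 134 subjects |
|---|---|---|
| 1 | 1 − 0.99 = 1% | 1.3 |
| 0.9 | 1 − 0.891 = 10.9% | 14.6 |
| 0.75 | 1 − 0.7425 = 25.8% | 34.5 |
| 0.5 | 1 − 0.495 = 50.5% | 67.7 |

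The documents do not give f. The Table 6 row that carries the note covers intra-procedure ballooning as well as planned later PTA, and ballooning during creation is not a secondary procedure (Protocol 9.8 and 9.11).

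**Step 4: the three readings side by side, for illustration.** The documents give no thrombosis or maintenance-intervention rate. Assume a 12-month thrombosis risk a of 10% to 30%, a 12-month risk b of a non-maturation intervention in an open access of 20% to 40%, and independence.

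- Qualifier on all verbs: 1 − a, from 90% down to 70%.
- Qualifier on the last verb, maturation exempt: (1 − a)(1 − b), from 0.9 × 0.8 = 72% down to 0.7 × 0.6 = 42%.
- Section 4 wording: at most 1 − 0.99f, before thrombosis and other interventions lower it further.

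At a = 20% and f = 0.5, the first and third readings differ by at least 80 − 50.5 = 29.5 points.

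**The case against.** The strongest reply is that a careful programmer would not go wrong. SAP 10.1 points to Section 7, so SAP 7.7.2 governs, Protocol 13.3.1 matches it, and the Section 4 texts are short summaries. Within 7.7.2 the qualifier naturally belongs to re-establishing patency, since facilitating or maintaining it presupposes an open access. The endpoint is secondary and descriptive, and Secondary Objective #3 reports interventions separately by type, indication, count and person-year rate, so no data are lost.

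Much of this stands. It lowers the severity and makes the Section 4 result less likely to be reported. It does not remove the defect, because the section that governs is the one holding the ambiguous phrase.

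A reader might infer three stronger things that the documents do not support:

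- *The analysis wording makes primary and assisted primary patency the same endpoint.* This holds only if the qualifier governs all three verbs, and the maturation exclusion and the subcomponent analysis argue against that intent.
- *The Section 4 wording drives primary patency to about 1%.* That figure is 1 − 0.99 and needs f = 1. The expectation of similar procedures after the index procedure supports a low value, not that specific one.
- *The readings span nearly 0% to 100%.* That pairs f = 1 with a thrombosis rate close to zero, and the documents give no thrombosis rate.

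**Conclusion.** The conflict is real and should be fixed. Two definitions are pre-specified in each document, and the one in the governing section contains a phrase that is at best misleading. Its size depends on the reading. Identity with assisted primary patency is exact under the broad attachment of the qualifier and absent under the narrow one. The Section 4 wording caps the 12-month estimate between 1% and 50.5% for f between 1 and 0.5, and higher for smaller f, provided that the pre-market maturation rate recurs and no exclusion is applied. Primary endpoints, sample size and error rates are unaffected.

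**What to change.** Use one definition in Protocol 4.1.4, Protocol 13.3.1, SAP 4.2.1 and SAP 7.7.2: the Section 4 text, with the addition that an intervention counts whether or not the access is thrombosed. Delete the thrombosed-access qualifier from the two analysis sections. Carry the existing maturation-procedure exclusion, unchanged, into the two endpoint lists. Add one sensitivity Kaplan-Meier row for primary patency without the exclusion, so that its effect is visible.

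This does not extend to requiring a recorded outflow below 400 ml/min for each excluded procedure. Duplex ultrasound is scheduled at study visits (Protocol Table 1), and neither document requires a flow measurement before each maturation procedure, so such a rule could turn undocumented maturation procedures into events.

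The cost is minor wording changes in both documents and one extra row. Reported primary patency will be lower than if the qualifier were applied to all three verbs.
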